## **Analysis of Percent Time in Range (% TIR)**

The primary outcome is % TIR for the control and AID. To compare the two groups, a linear regression model will be used using the covariates age, insulin treatment, baseline HbA1c, diabetes type, and site (random effect). The point estimate for difference in treatment effect, 95% confidence interval, and p-value for the mean % TIR difference will be reported. Summary statistics for each group will also be reported. Residuals will be checked for skewness and, if found to be highly skewed, a non-parametric or robust estimation method will be used.

## **Hierarchical Outcomes and the Hypothesis Testing Procedure**

### **Hierarchical Testing**

The hierarchical outcomes to be tested and their order is as follows:

1. % TIR (superiority)
2. Percent time >250 mg/dL (superiority)
3. Mean glucose (superiority)
4. Percent time <70 mg/dL (non-inferiority – 2.5% limit)
5. Percent time <70 mg/dL (superiority)

To preserve the over type I error rate, a hierarchical approach will be used. Hypothesis testing starts with the first outcome (TIR) and continues down the list unless/until a non-statistically significant result ( $p>0.05$ ) occurs. If one of the hypothesis tests results in  $p>0.05$ , then none of the remaining outcomes (if any) lower on the list will be formally tested. Summary statistics with 95% confidence intervals will be reported for all outcomes on the list regardless of statistical significance.

The primary safety outcome (% time <54 mg/dl) will be analyzed separately, with initial testing for non-inferiority followed by superiority, if appropriate. With a non-inferiority margin of 0.5% for % time <54 mg/dL [Null hypothesis (H0):  $\mu\delta \geq 0.5\%$ ] a sample size of 14 provides 90% power to confirm the lower limit of the 95% CI is above -0.5% (Alternate hypothesis (Ha):  $\mu\delta < 0.5\%$ ).

A robust regression method may be used for % time >300 mg/dL and % time <54 mg/dL as these metrics are most likely to be skewed away from normality. For glycemic variability, a linear regression model can be used; if highly skewed, a robust regression method can be used instead. Covariates used will be similar as those used in the primary outcome analysis.

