**Table 2. Sample size estimates**

Treatment Effect			
5%	10%	15%	20%
N=504	N=126	N=56	N=32

It should be noted, sample sizes are typically increased by 10-15% to account for potential dropout.

An N=100 gives a power of 99% to detect a difference of 15% between groups at a standard deviation of 16% (AIDING pilot) or 17.3% (prior trials) and  $\alpha=0.05$ . An N=56 gives a power of 90% to detect a difference of 15%. To include at least 20 participants in subgroups of interest (T1D, renal disease, and steroid exposure) for the exploratory analysis and at least 100 participants with  $\geq 48$  hours of device use for the efficacy and safety analysis, we will enroll a total of 120 participants with sufficient CGM data.

**CGM Data Sufficiency Definition:** A minimum of 70% of data per patient day and a minimum of 24 hours in sensor duration will serve as the thresholds for inclusion in the per-protocol analysis (Spanakis et al 2023).

**Table 3** shows the minimum detectable differences for a range of sample sizes.

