**Primary Safety Endpoint:**

- % TBR <54 mg/dl (non-inferiority followed by superiority)

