**Description of Statistical Methods**

**General Approach**

The intent-to-treat (ITT) approach will be used with each participant analyzed in the group to which they were randomized regardless of treatment received. A sensitivity (per-protocol) analysis

will also be conducted for participants with >24 and 48 hours of data. This analysis will assess the robustness of the primary findings to protocol adherence and sufficient exposure to AID.

All p-values, unless otherwise noted, will be two-sided. Percent time below 70 mg/dL and time below 54 mg/dL will initially be tested as non-inferior; if the alternative hypothesis is not rejected, these metrics will then be tested for superiority. Time below 54 mg/dL will be tested separately (primary safety endpoint).

It is expected % TIR will be normally distributed and can be assessed with a standard linear regression approach. If residuals are skewed, a nonparametric or robust regression approach will be used. Other outcomes not normally distributed will also be assessed using a nonparametric or robust regression approach. The outcomes most likely to be skewed from past experience are the % time below 70 mg/dL and 54 mg/dL.

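### The non-inferiority rule for the primary safety endpoint (% time <54 mg/dL) contradicts itself: the hypotheses and the confidence-limit criterion point in opposite directions, and delta is never defined

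*SAP*

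**What the plan says.** The SAP lists the primary safety endpoint as percent "TBR <54 mg/dl (non-inferiority followed by superiority"). The rule is in one sentence of Hierarchical Testing. It opens "With a non-inferiority margin of 0.5% for % time <54 mg/dL", prints H0: delta ≥ 0.5%, states that "a sample size of 14 provides 90% power to confirm the lower limit of the 95% CI is above -0.5" percent, and closes with Ha: delta < 0.5%. No SD is given for this endpoint, and the SAP nowhere says whether delta is AID minus control or control minus AID.

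Three related statements:

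- Step 4 of the hierarchy reads "Percent time <70 mg/dL (non-inferiority – 2.5% limit"), with no direction and no confidence limit.
- General Approach, on both hypoglycaemia metrics, says that "if the alternative hypothesis is not rejected, these metrics will then be tested for superiority".
- Hierarchical Testing says that once a test in the list fails, "then none of the remaining outcomes (if any) lower on the list will be formally tested".

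**The concern.** Less time below 54 mg/dL is better, so AID is inferior when it adds time there. The printed hypotheses and the written limit correspond to opposite subtractions:

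- **Delta = AID minus control:** the hypotheses are right and the limit is wrong.
- **Delta = control minus AID:** the limit is right and the hypotheses have the wrong sign.

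The two halves agree only if delta changes sign within the sentence, and the SAP does not say that it does. Someone must therefore decide which half to discard. As written, that decision can be made after data exist, in an open-label trial, for an endpoint tested outside the hierarchy. If the limit is programmed on AID minus control, an increase in time below 54 mg/dL would be declared non-inferior and a clear reduction would fail.

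Two smaller faults sit beside this. The General Approach gate speaks of not rejecting the alternative, but a test rejects or fails to reject the null. And the statement about 14 participants cannot be checked without an SD.

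**Working it through.** **Inputs from the SAP.** Margin 0.5 percentage points; two-sided 95% CI, hence one-sided 0.025; 1:1 allocation; stated sample size 14 at 90% power; planned 120 participants with sufficient CGM data, of whom at least 100 have 48 hours or more of device use. **Assumed:** the SD of percent time below 54 mg/dL.

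**Step 1: the SAP's own figure.** N=14 cannot be reproduced without an SD, so I solve for the SD it implies at zero true difference:

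SD = 0.5 / [(1.960 + 1.2816) × √(2/n per arm)]

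- 14 in total (7 per arm): 0.5 / (3.2415 × 0.5345) = 0.289; with the t distribution, 0.265.
- 14 per arm: 0.5 / (3.2415 × 0.3780) = 0.408; with the t distribution, 0.393.

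**Step 2: what each half tests.** Rejecting H0: delta ≥ +0.5 at one-sided 0.025 is the same as the upper 95% limit being below +0.5. A lower limit above -0.5 rejects H0: delta ≤ -0.5. These are mirror images, not the same test.

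**Step 3: how often each is met.** Take delta = AID minus control, 60 per arm, SE = SD × √(2/60), normal approximation:

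- P(lower > -0.5) = Φ((delta + 0.5)/SE - 1.96)
- P(upper < +0.5) = Φ((0.5 - delta)/SE - 1.96)

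SE is 0.0913, 0.1369 and 0.1826 at SD 0.5, 0.75 and 1.0.

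| True delta | Written limit (lower > -0.5) | Printed hypotheses (upper < +0.5) |
|---|---|---|
| +0.5 (AID worse) | >99.9% at all three SDs | 2.5% |
| -0.5 (AID better) | 2.5% | >99.9% at all three SDs |

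For example, at SD 1.0 and delta = +0.5: Φ(1.0/0.1826 - 1.96) = Φ(3.52) = 0.9998, against Φ(0 - 1.96) = 0.025.

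**Step 4: no true difference.** The CI half-width is at most 1.96 × 0.1826 = 0.358, below 0.5, so both criteria cannot fail together. They give opposite verdicts with probability 2 × [1 - Φ(0.5/SE - 1.96)]: 0.04%, 9% and 44% at SD 0.5, 0.75 and 1.0. At the SDs implied in Step 1 it is about 2 per million or less.

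**Step 5: skewed data.** The SAP expects this endpoint to be skewed. I simulated 40,000 trials with 60 per arm, 70% zeros and gamma values (shape 0.7) otherwise, and a 95% CI for the mean difference. With means of 0.8 (AID) and 0.3 (control), and SDs of about 2.1 and 0.8, the written limit passes 98% and the printed hypotheses 8%. With the means exchanged, the two results reverse.

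**Step 6: power at the planned size,** zero true difference, P = Φ(0.5/SE - 1.96):

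| Assumed SD | N=100 | N=120 |
|---|---|---|
| 0.5 | 99.9% | >99.9% |
| 0.75 | 92% | 95% |
| 1.0 | 71% | 78% |

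The largest SD that still gives 90% power (t distribution) is 0.76 at N=100 and 0.84 at N=120.

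**The case against.** The strongest reply is that the limit appears in a power statement, while the formal hypotheses around it are coherent under the usual AID minus control reading. The limit is then simply the same test written on control minus AID. A careful statistician would see the intended one-sided margin, and the contrast of >99.9% with 2.5% measures a misreading rather than an expected analysis. It is true that the intent can be guessed and that power at zero difference does not depend on direction. But the phrase "to confirm the lower limit of the 95% CI is above -0.5" percent is the only confidence-limit criterion the SAP gives for this endpoint. A reader who follows it on the natural contrast gets the wrong answer.

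Other parts of the reply stand to some degree:

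- **SD range.** If the SD is really 0.26 to 0.41, as N=14 implies, opposite verdicts at zero difference are negligible and power at N=100 exceeds 99.9%. The 9%, 44% and 71–78% figures depend on larger, assumed SDs. The reversal at a true difference of ±0.5 does not.
- **Total or per arm.** Table 3 is headed as total N and includes 14, so a total is the likelier reading. The missing SD remains.
- **The superiority gate.** Read charitably, it agrees with the ordering in Hierarchical Testing. Read as proceeding after non-inferiority fails, it conflicts with the stop rule for time below 70 mg/dL. Either way the effect on error rates is small, because superiority on the same CI (upper limit below 0) already implies non-inferiority.
- **Skewness.** In Step 5 the true difference sits exactly at the margin, and the correctly directed rule passes 8% rather than the nominal 2.5%. Correcting the direction does not settle which estimator should supply the CI.

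**Conclusion.** The concern holds, and the text must be corrected. The decision rule for the primary safety endpoint is wrong as written: its hypotheses and its confidence limit are incompatible under either definition of delta. This follows from the wording alone and needs no assumption. The consequence if the limit is applied to AID minus control is a near-complete reversal at a true difference equal to the margin (>99.9% against 2.5%), assuming 60 per arm, SD 0.5 to 1.0 and normality. In the skewed example it is 98% against 8%. This is a fault in the rule, not in the sample size. The gate wording and the uncheckable N=14 statement are secondary.

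**What to change.** In the SAP:

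1. Under Hierarchical Testing, define delta as AID minus control. Keep H0: delta ≥ 0.5% and Ha: delta < 0.5%, and declare non-inferiority for time below 54 mg/dL if the upper limit of the two-sided 95% CI is below 0.5%. Delete the lower-limit criterion.
2. State the same rule for step 4, time below 70 mg/dL, with 2.5%.
3. Under General Approach, say that superiority is tested only if the non-inferiority null hypothesis is rejected.
4. Replace the N=14 statement with power at the planned 100 to 120 participants, giving the assumed SD and its source.
5. Because robust regression is allowed for this endpoint, name the estimator and CI method to which the limit applies.

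The cost is SAP wording only; design, data and sample size do not change. The restated safety power may look less favourable than the printed 90%, for example 71% to 78% if the SD is 1.0 point.

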## **Insulin Analyses**

Average daily insulin units will be compared between the treatment groups in the same fashion as described for the primary outcome, as well basal insulin and bolus amounts.

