**Table 1. Study Summary**

Project Title	Automated Insulin Delivery for Inpatients with Dysglycemia (AIDING) Randomized Controlled Trial
Précis	This randomized controlled trial will test the efficacy and safety of automated insulin delivery (AID) in hospitalized patients with diabetes (type 1 or type 2) requiring insulin therapy who are admitted to general medical/surgical floors. Participants will be randomized to AID + remote CGM (intervention) or multiple daily insulin injections (MDI) + CGM (control group). Participants will be followed for a total of 10 days or until hospital discharge (if less than 10 days).
Study Design	Open label, multicenter, randomized (1:1), parallel-group, clinical trial.
Objectives	
Primary objective: To test the efficacy and safety of AID versus standard of care therapy in the inpatient setting.
 
Secondary objectives: To determine differences in CGM derived metrics between AID and standard of care therapy in the hospital and explore differences in treatment effect according to individual characteristics.

Research Intervention	The Omnipod 5 system, consists of a disposable insulin infusion pump (or “pod”), a built-in model predictive control (MPC) insulin dosing algorithm, and a remote smartphone interface (Controller), that interact with a Dexcom G7 continuous glucose monitor (CGM) to automatically control insulin delivery based upon real-time glucose values. The Controller component also enables remote interaction with the system, including glucose monitoring as well as insulin dosing management and adjustments. The control group will wear a Dexcom G7 CGM.
Treatment Groups	Participants will be randomized to AID + CGM or to MDI + CGM for up to 10 days or until hospital discharge.
Population	
Key Inclusion Criteria:
 
Any person <math>\geq 18</math> years of age with diabetes mellitus (except cystic fibrosis- and pregnancy-related) admitted to general (non-ICU)

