	
medical-surgical hospital services who requires inpatient insulin therapy (i.e.,T1D or T2D with <math>\geq 2</math> glucose values <math>\geq 180\text{mg/dl}</math>)
 
Key Exclusion Criteria:
 
 
• Patients admitted to ICU
 
• Patients anticipated to require less than 48 hours admission
 
• Current evidence of hyperglycemic crises (diabetes-related ketoacidosis or hyperosmolar hyperglycemic state)
 
• Severe anemia with hemoglobin <math><7\text{ g/dL}</math>
 
• Evidence of hemodynamic instability
 
• Hypoxia (<math>\text{SpO}_2 <92\%</math> on supplemental oxygen)
 
• Pre-admission or inpatient total-daily insulin dose <math>>150\text{ units daily}</math>
 
• Patients with T2D on correctional insulin therapy alone.
 
• Patients without diabetes with stress hyperglycemia (not related to steroids or medical nutrition therapy) and with <math>\text{HbA1c} <6.5\%</math>
 
• Patients on AID as outpatient
 
• Patients with a condition impeding their ability to consent or answer questionnaires
 
• Patients who are pregnant at time of enrollment
 
• Patients who are unable or unwilling to use rapid-acting insulin analogs (Humalog, Admelog, or Novolog during the study)
 
• Active use of a substance known to interfere with CGM accuracy, including hydroxyurea, high dose acetaminophen (<math>>4\text{ grams/day}</math>), or high dose ascorbic acid (<math>>500\text{ mg/day}</math>)
 

Sample Size	120 participants
Planned Enrollment	Up to 135 participants
Number of Sites	3
Endpoints	
Primary Endpoints:
 
Efficacy: time spent in glucose target range (TIR, 70-180 mg/dl)
 
Safety: time spent below range (TBR, <math><54\text{ mg/dl}</math>)
 
Key Secondary Endpoints:
 
Time spent above range (TAR <math>>250\text{ mg/dl}</math>)
 
Mean hospital glucose
 
TBR <math><70\text{ mg/dl}</math>
 
Other Secondary and Exploratory Endpoints:
 
Time spent above 180 mg/dl (TAR <math>>180\text{ mg/dl}</math>)
 
Time spent between 70-99 mg/dl

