**Other Secondary Outcomes – Insulin Analyses**

- Basal insulin
- Bolus amounts
- Total daily insulin dose

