## **Analysis Cohorts**

### **Safety Analyses**

All safety outcomes will be reported for all participants throughout the study.

Any baseline factors found to be imbalanced between treatment groups will be added as covariates to the analysis.

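### Daily insulin is compared in raw units without body size or baseline dose, which costs precision, and basal and bolus receive p-values although their split partly reflects delivery method

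*SAP*

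**What the plan says.** The SAP lists basal insulin, bolus amounts and total daily dose under "Other Secondary Outcomes – Insulin Analyses". The Insulin Analyses section gives the method: "Average daily insulin units will be compared between the treatment groups in the same fashion as described for the primary outcome". The same sentence then extends this method to the two components, with the words "as well basal insulin and bolus amounts". The outcome is therefore in units, with no scaling to body size.

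The method carried over is in Analysis of Percent Time in Range: "a linear regression model will be used using the covariates age, insulin treatment, baseline HbA1c, diabetes type, and site (random effect"). That section reports a point estimate, a 95% confidence interval and a p-value, so the insulin outcomes inherit a between-arm p-value each.

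Three other places bear on the point:

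- Table 1 (Research Intervention) describes the AID system as working "to automatically control insulin delivery based upon real-time glucose values". Controls receive multiple daily injections.
- Table 1 (Key Exclusion Criteria) excludes people above 150 units daily on "Pre-admission or inpatient total-daily insulin dose", so a dose has to be looked at during screening. Baseline Descriptive Statistics lists BMI and diabetes treatment, but no insulin dose.
- Under Analysis Cohorts, Safety Analyses, the SAP adds: "Any baseline factors found to be imbalanced between treatment groups will be added as covariates to the analysis".

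The SAP does not define basal or bolus for either arm.

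**The concern.** There are two separate issues.

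**Precision of the total.** The covariates were chosen for % TIR. For an outcome measured in insulin units, the natural prognostic variables are body size and the dose the person was already on. Eligible people may take anything up to 150 units a day, so raw doses can spread widely. Leaving out variables that explain part of that spread widens the interval for total daily insulin for no benefit.

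**Meaning of the split.** Insulin that an algorithm adjusts continuously to glucose has no direct counterpart in an injection regimen. Whichever label that insulin carries helps to determine how much is counted as basal and how much as bolus in the AID arm. Randomisation does not remove this, because it concerns how the outcome is constructed in each arm. A significant difference in basal or bolus could then be read as a change in insulin need when part of it is only the way insulin was delivered.

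**Working it through.** **Plan's own figures.** The SAP gives no SD, target difference or power for insulin. Its nearest figures are those for % TIR. With power = Φ(d / (SD·√(4/N)) − 1.96), d = 15 and N = 100, the result is 0.991 at SD 17.3% (SAP Table 4: 0.990) and 0.997 at SD 16% (0.997). At N = 56 it is 0.9005 and 0.939 (0.901 and 0.939). The sample sizes in SAP Table 2 (504, 126, 56, 32) also reproduce. This point affects none of them.

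**Inputs for total daily insulin.** N = 120, 1:1, two-sided 5%, from the SAP sample size sections. Results are in units of the residual SD left by the planned covariates, because no insulin SD is given. R is the partial correlation of body size and baseline dose, taken together, with on-study dose, given those covariates. It is an assumption, shown from 0.3 to 0.8.

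**Formulas.** SE ratio = √(1 − R²). 95% half-width = 1.96 × √(4/120) × √(1 − R²). Equivalent unadjusted N = 120 / (1 − R²). Power is shown for an illustrative difference of 0.4 SD.

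| R | SE ratio | SE reduction | Half-width (SD) | Equivalent N | Power at 0.4 SD |
|---|---|---|---|---|---|
| 0 | 1.000 | none | 0.358 | 120 | 0.59 |
| 0.3 | 0.954 | 5% | 0.341 | 132 | 0.63 |
| 0.5 | 0.866 | 13% | 0.310 | 160 | 0.72 |
| 0.7 | 0.714 | 29% | 0.256 | 235 | 0.87 |
| 0.8 | 0.600 | 40% | 0.215 | 333 | 0.96 |

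**Bias or noise?** In 4,000 simulated trials of 120 per value of R, with no true difference, the mean unadjusted estimate was 0.006, −0.004, 0.004 and 0.001 SD at R = 0.3, 0.5, 0.7 and 0.8. Its SE was 0.181, 0.180, 0.185 and 0.187. With adjustment the SE was 0.175, 0.159, 0.132 and 0.110. Omitting the covariates costs precision and introduces no bias.

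**Part-days.** The SAP does not say how the daily average is formed over an incomplete day. Suppose basal were injected once every 24 hours and the doses in a window of L hours were divided by L/24 (both assumptions). With a random start and fractional day f, the SD of the captured rate is √(f(1 − f)) / (L/24):

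- 36 h: one or two doses over 1.5 days, so 67% or 133% of the true rate; SD 0.5/1.5 = 33%.
- 60 h: two or three doses over 2.5 days, so 80% or 120%; SD 0.5/2.5 = 20%.
- 132 h: SD 0.5/5.5 = 9%.
- 48 h and 240 h: f = 0, so no error.

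The mean is right in every case, so this too is noise. It shrinks with length of stay.

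**Basal and bolus.** No arithmetic applies. Insulin Analyses together with the % TIR section gives a p-value on each component. Table 1 makes delivery in one arm automated and glucose-responsive, and in the other arm it is by injection. With no definition by arm, the share assigned to each label depends partly on the method of delivery.

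**The case against.** Some of the case on the other side stands.

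- **Total daily insulin is a fair comparison.** A reader might infer that all the insulin results fail to compare like with like. The documents do not support that. Units per day are the same quantity in both arms, and random allocation keeps the raw contrast unbiased. The comparability problem is confined to the basal/bolus split.
- **The labelling is not in the SAP.** It says that the AID system adjusts delivery to glucose, but not that this insulin is recorded as basal, nor that correction insulin in controls is recorded as bolus. The protocol may define both. Describing how insulin was delivered is legitimate for a trial of a delivery system. This limits the point to interpretation: the direction and size of any artefact cannot be stated.
- **The covariate gap is not absolute.** The insulin-treatment term might mean pre-study insulin, and an imbalance in BMI would bring BMI in. Neither route secures the gain. The term is undefined and could mean the randomised arm, since no other arm term is named; if it does mean pre-study insulin, it may record use rather than dose. The imbalance rule depends on the data, has no criterion, and cannot act on a baseline dose that is not tabulated.
- **Underpowered cannot be shown.** A reader might infer it, but the SAP gives no SD, target difference or power goal for insulin.
- **The part-day figures are worst cases.** Both the 36 h and 60 h examples use a half-day remainder. The first lies below the 48-hour minimum follow-up in Statistical Hypotheses, although the Sample Size section expects some people not to complete 24 hours.

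**Conclusion.** The point holds in limited form. The planned comparison of total daily insulin is valid but less precise than it need be. The loss is about 5% to 40% of the standard error if the partial correlation is 0.3 to 0.8; that range is an assumption, and the documents cannot narrow it. The correlation has to be the partial one: a raw correlation between baseline and on-study dose could overstate the gain, because diabetes type, HbA1c and the other planned covariates may already explain part of it.

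The between-arm p-values on basal and bolus are hard to interpret, because a difference would partly reflect delivery method. By how much depends on definitions that the SAP does not give.

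The consequence is modest. The insulin outcomes are other secondary outcomes outside the testing hierarchy. The % TIR and hypoglycaemia conclusions and the sample size are unaffected. The change is worth making because it costs little.

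**What to change.** Amend the Insulin Analyses section as follows:

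1. Make total daily insulin the tested insulin outcome, either in units/kg/day or in units with BMI or weight as a prespecified covariate.
2. Add pre-randomisation total daily dose as a prespecified covariate where it is recorded, and state how missing values are handled so that nobody leaves the ITT analysis for lack of one.
3. Report basal and bolus amounts by arm descriptively, with the definition used in each arm (including where automated delivery and correction insulin are counted) and no between-arm p-value.
4. Divide by actual exposure time. Use complete 24-hour periods only as a sensitivity analysis, so that short-stay participants remain in the ITT set.

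This is a change of SAP wording. Two tests become descriptive. BMI is already collected, but a baseline dose is only known to be examined at screening and may be missing for some participants. No sample size or primary analysis text has to change.
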